Guidelines for dose adjustments of neratinib in the event of abnormalities in LVEF are shown in **Table A2.5**. LVEF assessments will be performed according to the Schedule of Procedures ([Appendix 1](#)). It is strongly recommended to use the same method of cardiac evaluation (ECHO or MUGA) at each time point for each patient.

Table A2.5: Left Ventricular Ejection Fraction (LVEF) Results Requiring Dose Adjustments of Neratinib

EVENT ON DAY OF SCHEDULED TREATMENT	Action
Asymptomatic absolute decline of LVEF $\geq 15\%$ from baseline OR absolute decline of LVEF $\geq 10\%$ ad below the lower limit of normal of 50%	
A) If LVEF is below 40%: hold neratinib and seek cardiology input OR continue neratinib with great caution.
 
Initiate monthly monitoring of LVEF
 
 • If while monitoring monthly, LVEF remains <40%: reconsider neratinib only if appropriate and after cardiology consult. • If while monitoring monthly, LVEF increases to $\geq 40\%$: continue neratinib, monitor LVEF every 12 weeks and consider cardiac support with input from cardiologist 
B) If LVEF is between 40% to 50%: continue neratinib with caution and surveillance.
 
Initiate monthly monitoring of LVEF.
 
 • If while monitoring, LVEF falls to <40%: Follow bullet point A instructions described above. • If while monitoring, LVEF remains $\geq 40\%$: continue neratinib, monitor LVEF every 12 weeks and consider cardiac support with input from cardiology.
Symptomatic cardiac failure	
 • Neratinib should be discontinued.

Abbreviations: LVEF: left ventricular ejection fraction.

If a patient has a second episode of asymptomatic decline in LVEF that meets either of the above criteria, permanently discontinue **neratinib**, repeat LVEF in 3-4 weeks and consider cardiology consult.

Note that, for AEs other than symptomatic LVEF decline, if **neratinib** is held for >28 days, the patient should be withdrawn from the active treatment phase of the study (see [Section 10.1](#)). In case of asymptomatic LVEF decline, patients may resume **neratinib** within 1 week after LVEF recovery is documented as above, even if the timeframe exceeds 3 weeks. If a site does not provide normal ranges for ECHO or MUGA, a lower limit of normal of 50% should be used.

Hematologic Toxicity

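### The LVEF note in Appendix 2 exempts symptomatic instead of asymptomatic decline from the 28-day withdrawal rule, and so contradicts its own next sentence

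*Protocol*

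**What the plan says.** All of the LVEF text is in Protocol Appendix 2, under Left Ventricular Ejection Fraction Toxicity.

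- **Note under Table A2.5, first sentence.** It opens with "Note that, for AEs other than symptomatic LVEF decline, if" and goes on to the consequence: once the drug "is held for >28 days, the patient should be withdrawn from the active treatment phase of the study". It refers the reader to Section 10.1.
- **Same note, second sentence.** "In case of asymptomatic LVEF decline, patients may resume" the drug, and the time allowed for this is "within 1 week after LVEF recovery is documented as above, even if the timeframe exceeds 3 weeks".
- **Table A2.5, asymptomatic decline, bullet A (LVEF below 40%).** The investigator may "hold neratinib and seek cardiology input OR continue neratinib with great caution". LVEF is then checked monthly. If it reaches 40% or more, neratinib continues. If it stays lower, neratinib may be reconsidered after a cardiology consult.
- **Table A2.5, bullet B.** "B) If LVEF is between 40% to 50%: continue neratinib with caution and surveillance".
- **Table A2.5, symptomatic cardiac failure.** "Neratinib should be discontinued".

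Three other places set the weight of these rules. Section 6.1.1 makes the dose adjustment guidelines the least an investigator must do, and bars restarting a product once it has been discontinued. Section 10.1 brings in the Appendix 2 stopping circumstances unless the Medical Monitor agrees otherwise. Its own 28-day bullet covers only holds due to an SAE and allows resumption with advance Sponsor approval.

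**The concern.** The two sentences of the note stand side by side and give opposite answers for the same patient. The first withdraws everyone held for more than 28 days unless the reason is symptomatic LVEF decline. The second lets asymptomatic patients resume after recovery, however long that took.

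The exemption also points the wrong way. Patients with symptomatic cardiac failure are discontinued under the table, so they have no hold that could need exempting. The patients who are held, monitored and expected to recover are the asymptomatic ones. The word *asymptomatic* appears three other times in this part of the appendix, including in the very next sentence, so *symptomatic* looks like a slip.

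At stake is whether a recovered patient goes back on cancer treatment or leaves the active phase. Because reintroduction after discontinuation is barred, a site that follows the first sentence may not be able to reverse it. Two sites could also treat the same case differently.

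**Working it through.** The plan has no figure to reproduce here. The check is of rule logic, with some day counting.

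**Step 1. Apply both sentences to an asymptomatic patient with documented recovery.** Let h be the length of the hold in days.

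| h (days) | First sentence (withdraw if h > 28) | Second sentence | Conflict |
|---|---|---|---|
| 20 | no | may resume | no |
| 22 | no | may resume | no |
| 28 | no | may resume | no |
| 29 | yes | may resume | yes |
| 35 | yes | may resume | yes |
| 60 | yes | may resume | yes |

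The two rules agree up to day 28 and conflict at every longer hold.

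**Step 2. When would a hold pass 28 days?** Let r be the hold day of the scan that documents recovery, and d the days from that scan to restart. The second sentence allows one week, so d = 0 to 7 and h = r + d.

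- r of 21 or less: the longest hold is 21 + 7 = 28, so there is no conflict.
- r from 22 to 28: it depends on the restart day. At r = 25, 25 + 3 = 28 is clear and 25 + 4 = 29 conflicts.
- r of 29 or more: always in conflict.

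The Protocol does not say how hold days are counted. If the first missed dose is hold day 1 and the restart day is not counted, h = r + d - 1 and each boundary moves one day later (22, 23 to 29, 30). These counts show where the conflict lies. They are not probabilities, and a site can choose a restart day that avoids it when r falls in the middle band.

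**Step 3. Link to the monitoring schedule.** Assume that monthly means 28 to 31 days. Recovery at the first monthly scan then gives a hold between 28 + 0 = 28 and 31 + 7 = 38 days, or 27 to 37 under the other count. An earlier unscheduled scan, which Section 9 allows, would shorten it.

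**Step 4. Worked case.** Baseline LVEF is 60%. At Cycle 3 Day 1 it is 38%, a fall of 22 points, and neratinib is held under bullet A. A scan on hold day 30 shows 44%, read here as recovery because bullet A continues neratinib at 40% or more. Restart falls on hold day 30 to 37, which is more than 28 days under either count. The first sentence says withdraw; the second sentence and bullet A say treat.

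**Step 5. After the one-word change.** With *asymptomatic* in the first sentence, this patient is exempt from the 28-day rule in the note and the second sentence governs. The conflict within the note disappears at every h.

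**The case against.** The strongest reply is that sites would know what to do. The second sentence is the more specific text, and bullet A supports it by contemplating treatment after a monthly scan. The first sentence says *should* and points to Section 10.1, where the 28-day bullet covers only SAEs and the Medical Monitor can agree otherwise. This stands as a limit on practical harm. It does not reconcile the note: a case-by-case exception is not a rule, and the second sentence seems written to make exceptions unnecessary.

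The table speaks of symptomatic cardiac failure and the note of symptomatic LVEF decline, and the documents do not equate them. That is fair. If the second is a milder state, though, the looser time limit goes to the patients with symptoms, which is no better.

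A letter lost in PDF reading cannot be fully excluded; the same table shows *ad* for *and*. But *symptomatic* is a clean whole word and nothing shows that it was misread.

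A reader might infer three stronger points, and the documents do not support them:

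- **The 3-week wording is a second conflict.** It is not. A hold that exceeds 3 weeks includes one that exceeds 28 days, so the mismatch is untidy but changes nothing operative.
- **Section 10.1 needs a matching exception.** Its 28-day bullet applies only to SAEs. An exception there would remove the advance Sponsor approval now required before a patient with a serious decline resumes.
- **A fall of 15 points or more that leaves LVEF above 50% is an unsafe gap.** No action is listed for it, and in whole points it needs a baseline of at least 51 + 15 = 66%. But with no adjustment listed the default is to continue, with scans as clinically indicated, and any added line would say just that. A repeat is already covered: "If a patient has a second episode of asymptomatic decline in LVEF that meets either of the above criteria, permanently discontinue" neratinib. This is a missing detail.

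**Conclusion.** The contradiction is real on the current text and the exemption names the wrong group. It sits in an operative dosing rule, so it is worth correcting, but its reach is minor:

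- 3-5 patients are to be enrolled.
- On-treatment LVEF is scheduled only in metastatic disease (Table A1.2, note m). Stage 1 to 3c patients are scanned after screening only if clinically indicated (Table A1.1, note m).
- The hold below 40% is optional, and bullet B continues neratinib.
- The colon biopsy, Cycle 1 diarrhea and inflammatory marker analyses do not depend on this rule.

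The documents give no rate of LVEF decline, so no expected number of affected patients can be stated. The onset of the conflict beyond day 28 follows from the text alone. The 28-to-38-day hold rests on the assumed meaning of monthly and shifts by a day with the counting convention. That *asymptomatic* was intended is an inference from the surrounding text, though a strong one. A reader should not conclude that the Protocol simply forces recovered asymptomatic patients off treatment; it gives both instructions.

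**What to change.** In the note under Table A2.5:

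1. First sentence: replace *symptomatic* with *asymptomatic*, so that the 28-day withdrawal rule applies to all AEs other than asymptomatic LVEF decline.
2. Second sentence: replace *3 weeks* with *28 days*, so that both sentences use one limit. This is for consistency only.

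Leave Section 10.1 unchanged. A non-serious asymptomatic decline would then follow the second sentence, and a hold of more than 28 days due to an SAE would still need advance Sponsor approval before resumption. No new line for LVEF above 50% is required.

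The cost is one word and one time limit, carried in the next protocol amendment. It adds no visit, scan or analysis, leaves the second-episode stop as it is, and needs no change to the SAP.

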4. INVESTIGATIONAL PLAN

4.1. Overall Study Design

This is an open-label, phase 2 study that will investigate colon pathology in patients with HER2-positive breast cancer treated with neratinib as monotherapy.

All patients will receive neratinib for the first 28 days as a single daily dose of 240mg.

Following the second study colonoscopy procedure:

- For patients being treated for stage 1 to 3c breast cancer in the extended adjuvant setting, neratinib will continue to be administered at a single daily dose of 240mg until completion of one year of therapy from start of treatment, or until disease recurrence (as determined by the Investigator), death, unacceptable toxicity, or other specified withdrawal criterion.
- For patients being treated for metastatic breast cancer (mBC), capecitabine will be introduced after the second study colonoscopy procedure at a dose of 750mg/m² twice daily for 14 days of each 21 day treatment cycle, with neratinib administered continuously throughout at 240mg daily, until disease progression, death, unacceptable toxicity, or other specified withdrawal criterion.

All patients will receive loperamide diarrhea prophylaxis daily for one (1) 28-day cycle and then as needed.

Following a 28-day screening period ([Section 9.1](#)), eligible patients will be enrolled. Baseline assessments will be performed prior to Cycle 1/Day 1 dosing. Patients will then participate in the active treatment phase, consisting of, in both groups, a single 28-day cycle of neratinib monotherapy ([Section 9.2](#)). Neratinib and loperamide will be administered orally by patients as described in [Section 6](#). The morning dose of neratinib will be held on the day of the second study colonoscopy procedure ([Section 6.1](#)).

Colonoscopy will be performed after eligibility has been confirmed, but prior to administration of the first dose of neratinib on Day 1 of Cycle 1, and at Day 30 (\pm 3 days). Thereafter, extended adjuvant patients with stage 1 to 3c breast cancer will continue to receive neratinib monotherapy for 1 year or until progression of disease, death, or intolerance to study prescribed therapy. Patients with mBC will continue to receive neratinib in 21-day cycles, beginning in Cycle 2, after completion of the second study colonoscopy procedure, in combination with capecitabine administered on Day 1-14 of each cycle, until progression of disease, death, or intolerance to study prescribed therapy.

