5.2. Exclusion Criteria

A patient will be excluded from this study if she/he meets any of the following criteria.

1. Patients with confirmed stage 1 through stage 3c breast cancer currently receiving chemotherapy, radiation therapy, immunotherapy, or biotherapy for breast cancer.
2. Patients with mBC that have received prior capecitabine or HER2 directed TKI therapy.
3. Currently using drugs that have been implicated as causing microscopic colitis/watery diarrhea, such as acarbose, aspirin, proton pump inhibitors, nonsteroidal anti-inflammatory drugs (NSAIDs), histamine H₂-receptor antagonists, selective serotonin reuptake inhibitors, and ticlopidine ([Pardi, 2017](#)).
4. Major surgery within <28 days of starting treatment or received chemotherapy, investigational agents, or other cancer therapy, except hormonal therapy (eg, tamoxifen, aromatase inhibitors), <14 days prior to the initiation of investigational products.
5. Active uncontrolled cardiac disease, including cardiomyopathy, congestive heart failure (New York Heart Association functional classification of ≥ 2 ; including individuals who currently use digitalis, beta-blockers, or calcium channel blockers specifically for congestive heart failure), unstable angina, myocardial infarction within 12 months of enrollment, or ventricular arrhythmia.
6. QTc interval >0.450 seconds (males) or >0.470 (females), or known history of QTc prolongation or Torsade de Pointes (TdP).
7. Diagnosis of inflammatory bowel disease.
8. Screening laboratory assessments outside the following limits:

Laboratory Parameters	Required Limit for Exclusion
Absolute neutrophil count (ANC)	$\leq 1,000/\mu\text{l}$ ($\leq 1.0 \times 10^9/\text{L}$)
Platelet count	$\leq 50,000/\mu\text{l}$ ($\leq 100 \times 10^9/\text{L}$)
Hemoglobin	$\leq 8 \text{ g/dL}$ (transfusions allowed) Transfusions must be at least 14 days prior to initiation of treatment
Total bilirubin	$>1.5 \times$ institutional upper limit of normal (ULN) (in case of known Gilbert's syndrome, $<2 \times$ ULN is allowed)
Aspartate aminotransferase (AST) and/or alanine aminotransferase (ALT)	$>2.5 \times$ institutional ULN ($>5 \times$ ULN if liver metastases are present in mBC patients)
Creatinine	Creatinine clearance $<30 \text{ mL/min}$ (as calculated by Cockcroft-Gault formula ^a or Modification of Diet in Renal Disease [MDRD] formula ^b)
International Normalized Ratio (INR)	≥ 1.5

^a [Cockcroft and Gault, 1976](#)

^b [Levey et al, 1999](#)

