6. ADMINISTRATION OF NERATINIB AND LOPERAMIDE TREATMENTS

6.1. Neratinib

Neratinib will be supplied as 40-mg, film-coated tablets packaged in bottles with desiccant.

Neratinib (240 mg; provided as six 40-mg tablets) will be self-administered orally by patients on a daily basis, starting with Cycle 1/Day 1. Neratinib must be taken with food, preferably in the morning.

In patients with stage 1 to 3c disease, extended adjuvant treatment with neratinib will be given continuously as a single 28-day cycle followed by continuous daily dosing for up to 1 year

In patients with mBC, following completion of a 28-day cycle of neratinib monotherapy and completion of the second study colonoscopy procedure, neratinib will be given continuously in 21-day cycles in combination with capecitabine. On the day of the second study colonoscopy procedure in both groups, the morning dose of neratinib will be held. Neratinib will be resumed the day following the second study colonoscopy procedure. In both groups, daily dosing should continue until disease recurrence or progression (as determined by the Investigator), death, unacceptable toxicity, or other specified withdrawal criterion is met (see [Section 10](#)).

During the first 28 days, patients must use a diary to record their intake of neratinib (see [Section 8.5.2](#)).

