6.3. Capecitabine

Patients with mBC will receive capecitabine, beginning in Cycle 2 of treatment (i.e., following completion of the second study colonoscopy procedure and biopsy).

Capecitabine is available at 150 mg and 500 mg film-coated tablets.

Capecitabine (total dose of 1500 mg/m² daily, administered as 750 mg/m² in approximately evenly divided doses) will be self-administered orally by patients starting with Cycle 2/Day 1 (i.e. following completion of the second study colonoscopy procedure and biopsy). Doses are to

be taken daily on Days 1 to 14 of each 21-day cycle. Capecitabine should be taken with water within 30 minutes after a meal.

During treatment with neratinib plus capecitabine, patients should be monitored for conditions that may require dose to be held or discontinued as described in [Appendix 2](#). Careful attention should be paid to the onset of diarrhea or hand-foot syndrome in particular, and early dose adjustment or prophylactic therapy should be implemented as described in [Appendix 2](#).

Daily dose of neratinib plus capecitabine should continue until a criterion for treatment withdrawal or study withdrawal is met (see [Section 10.1](#) and [Section 10.2, respectively](#)).

Refer to the capecitabine (Xeloda®) [US Package Insert](#) and/or the [SPC](#) for further information on dosing, safety assessments and toxicity management.

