8.2.3. Laboratory Assessments

Laboratory testing will be performed in accordance with the Schedule of Procedures ([Appendix 1](#)).

The institutional laboratory will analyze all laboratory endpoints from samples collected.

Screening laboratory results may be accepted as the baseline assessment if they are performed within 72 hours of initiation of enrollment.

The following laboratory endpoints will be determined, as summarized in [Table 7](#).

Table 7: Laboratory Parameters

Hematology	Hematocrit (Hct) Hemoglobin (Hb) Platelet count Red blood cell (RBC) count White blood cell (WBC) count, with differential	
Clinical chemistry	Albumin Alkaline phosphatase ALT AST Blood urea nitrogen (BUN) Calcium Chloride Creatinine Glucose (non-fasting)	Lactate dehydrogenase (LDH) Magnesium Phosphorus Potassium Sodium Total bilirubin Serum lipase Serum amylase

Table 7: Laboratory Parameters (Continued)

Hematology	Hematocrit (Hct) Hemoglobin (Hb) Platelet count Red blood cell (RBC) count White blood cell (WBC) count, with differential
Serum or urine pregnancy test	In women of child-bearing capacity (at screening and second test within 72 hours prior to C1D1).
Coagulation	International Normalized Ratio (INR)
Inflammatory markers	ESR, CRP, fecal calprotectin, fecal elastase

All clinically important abnormal laboratory tests occurring during the study will be repeated at appropriate intervals until they return either to baseline or to a nonclinically significant level deemed acceptable by the Investigator and the Sponsor Medical Monitor (or his/her designated representative), or until a diagnosis that explains them is made.

Criteria for reporting abnormal laboratory values as AEs are summarized in [Section 13.1.2](#).

The total volume of blood collected from each patient during the course of the study will be dependent upon the number of treatment cycles the patient completes. For patients receiving neratinib as monotherapy in the adjuvant setting who complete 1 year of treatment, approximately 50 mL of blood, corresponding to approximately 15 mL blood during screening, 15 mL on Day 1/Cycle 1 and 5 mL blood approximately every 3 months up to 1 year will be sampled. For patients with mBC, 15 mL of blood will be sampled at screening and on Day 1 of each treatment 21-day treatment cycle.

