Patients with baseline neutrophil counts of $<1.5 \times 10^9/L$ and/or thrombocyte counts of $<100 \times 10^9/L$ should not be treated with **capecitabine**. If unscheduled laboratory assessments

during a treatment cycle show Grade 3 or 4 hematologic toxicity, treatment with **capecitabine** should be held.

Guidelines for dose adjustments of capecitabine for hematologic toxicity due to combination of neratinib plus capecitabine are shown in **Table A2.6**.

Table A2.6: Hematologic Abnormalities Requiring Dose Adjustment of Capecitabine (When Administered in Combination with Neratinib)

NCI CTCAE v 4.0	Action
Grade 3 Neutrophil: <1000-500/mm ³ ; <1-0.5 x 10 ⁹ /L Platelet: <50,000-25,000/mm ³ ; <50-25 x 10 ⁹ /L Hemoglobin decreased: <8 g/dL; <4.9 mmol/L; <80 g/L; transfusion indicated	
 • Neratinib should be continued at the same dose • Hold capecitabine until event resolves or decreases to Grade 1 or Grade 2 • Reduce next capecitabine dose to 1100 mg/m² (550 mg/m² BID) • If the event recurs a 2nd time, hold capecitabine until event resolves or decreases to Grade 1 or Grade 2 • Reduce next capecitabine dose of 750 mg/m² (375 mg/m² BID) • If the event recurs/persists, discontinue capecitabine permanently.
Grade 4 Neutrophil: <500/mm ³ ; <0.5 x 10 ⁹ /L Platelet: <25,000/mm ³ ; <25 x 10 ⁹ /L Hemoglobin decreased: life-threatening consequences; urgent intervention indicated	
 • Neratinib should be continued at the same dose. • Capecitabine should be discontinued permanently OR if the Investigator deems it to be in the patient's best interest to continue, hold capecitabine until resolved to Grade ≤ 1 • If the Investigator decides to resume capecitabine, reduce the dose to 750 mg/m² (375 mg/m² BID) • If the event recurs/persists, discontinue capecitabine permanently

Abbreviations: BID: twice daily; L=liter; NCI CTCAE v 4.0: National Cancer Institute Common Terminology Criteria for Adverse Events Version 4.0.

Hand and Foot Syndrome

Guidelines for dose adjustments of neratinib and capecitabine for toxicity of Hand and Foot Syndrome (Palmar-Plantar Erythrodysesthesia syndrome) due to combination of neratinib plus capecitabine are show in **Table A2.7**.

Table A2.7: Hand and Foot Syndrome (Palmar-Plantar Erythrodysesthesia Syndrome) Requiring Dose Adjustment of Neratinib and Capecitabine

NCI CTCAE v4.0	Action

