3. DEFINITIONS

Baseline

The baseline value for a parameter of interest is the last measurement obtained prior to or on the date of the first dose of neratinib.

Cycle

The first cycle is 28 days for all subjects, all of whom receive neratinib and loperamide prophylaxis. After the first 28-day cycle, stage 1 to 3c breast cancer patients receiving extended adjuvant treatment return to clinic every 3 months. Metastatic breast cancer patients return to clinic at scheduled 21-day cycles, during with time they receive both neratinib and capecitabine.

Study Day 1

Study Day 1 is the date the first dose of neratinib is taken.

Treatment duration

Treatment duration in days = last dose date - first dose date + 1

Actual Dose Intensity

The actual dose intensity is defined as the cumulative actual dose divided by treatment duration.

Relative Actual Dose Intensity

The relative actual dose intensity is defined as the actual dose intensity divided by the planned dose intensity.

Prescribed Dose Intensity

The prescribed dose intensity is defined as the cumulative prescribed dose divided by treatment duration.

Treatment-Emergent Adverse Event (TEAE)

A TEAE is defined as an AE that occurs or worsens on or after the first administration of neratinib and up to 28 days after the second colonoscopy in patients with stage 1 to 3c breast cancer, and following completion of Cycle 2 in mBC patients.

Investigational Product (IP)

Investigational product (IP) is used to reference neratinib and capecitabine.

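### Criterion 8 admits metastatic patients with blood counts at which Appendix 2 bars capecitabine, the drug assigned to them from Cycle 2

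*Protocol*

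**What the plan says.** **Entry.** Exclusion criterion 8 (Protocol synopsis and Section 5.2) excludes a screening ANC of 1,000/µl or less, which it also gives as 1.0 x 10^9/L. It excludes platelets of 50,000/µl or less, and beside that prints 100 x 10^9/L. Neither row has a separate limit for mBC.

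**Assignment.** Section 6.3: "Patients with mBC will receive capecitabine, beginning in Cycle 2 of treatment". Section 4.1 says the same. Neither section states a blood count that must be met before capecitabine starts, although Section 6.3 refers to Appendix 2 for conditions that call for a hold or discontinuation.

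**Treatment bar.** Appendix 2, under Hematologic Toxicity: "Patients with baseline neutrophil counts of $<1.5 \times 10^9/L$ and/or thrombocyte counts of $<100 \times 10^9/L$ should not be treated with capecitabine".

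**Baseline.** Appendix 2 does not define the word. Section 4.1: "Baseline assessments will be performed prior to Cycle 1/Day 1 dosing". Section 8.2.3: "Screening laboratory results may be accepted as the baseline assessment if they are performed within 72 hours of initiation of enrollment". SAP Section 3 takes the "last measurement obtained prior to or on the date of the first dose of neratinib".

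**Neratinib.** Section 6.1: "In both groups, daily dosing should continue until disease recurrence or progression".

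**The concern.** The entry rule and the treatment rule use different count thresholds, and the entry rule is the looser one. An mBC patient can meet every numeric entry limit while holding a baseline count that already rules out half of the assigned regimen.

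What is at stake is the individual patient's course, not the trial's data. The patient would undergo two study colonoscopies with biopsies and take 28 days of neratinib alone, as a lead-in to a combination that could not be given. No replacement is available on study: Section 7.3 prohibits other chemotherapy, and Section 10.1 makes starting other anticancer therapy a reason to stop investigational product.

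**Working it through.** No sample size, power or error-rate figure is involved, because Section 12.5 sets the 3-5 patients by feasibility. The check is a unit conversion, a comparison of ranges, and a reading of what baseline means.

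**1. Units.** 1 cell/µl = 10^6 cells/L.
- ANC: 1,000/µl = 1.0 x 10^9/L. The two printed figures agree.
- Platelets: 50,000/µl = 50 x 10^9/L, whereas 100 x 10^9/L = 100,000/µl. The two printed figures differ by 100/50 = 2-fold.

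**2. Ranges (x 10^9/L), admitted at entry against barred from capecitabine.**

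| Count | Admitted | Barred | Admitted and barred | Width |
|---|---|---|---|---|
| ANC | >1.0 | <1.5 | >1.0 and <1.5 | 1.5 - 1.0 = 0.5 |
| Platelets, if 50,000/µl governs | >50 | <100 | >50 and <100 | 100 - 50 = 50 |
| Platelets, if 100 x 10^9/L governs | >100 | <100 | none | 0 |

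The ANC gap follows directly from the text. The platelet gap depends on which printed figure a site applies.

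**3. Which baseline?**
- *For the pre-neratinib value:* Section 4.1 places baseline assessments before Cycle 1/Day 1 dosing. Section 8.2.3 lets screening laboratory results serve as baseline. The SAP ties baseline to the first neratinib dose. Table A1.2 marks no CBC at Cycle 2/Day 1, and its CBC footnote names only screening and Cycle 1/Day 1, plus testing when clinically indicated.
- *For a pre-capecitabine value:* Section 8.2.3 also has 15 mL of blood drawn from mBC patients on Day 1 of each 21-day cycle, and Cycle 2 is such a cycle. Section 12.3 lists laboratory results at Cycle 2. The CBC footnote asks that CBC visits be aligned with liver function tests where possible, and those are due on Day 1 of every cycle.

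The first reading is the more natural. The second stays open.

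**4. Exposure before capecitabine is due.** Two colonoscopies, with the second at Day 30 ± 3 (Day 27 to 33), and 28 days of neratinib at 240 mg.

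**5. Effect on endpoints.** The biopsy endpoint, Cycle 1 diarrhea and the change in inflammatory markers are all complete by the second colonoscopy, and capecitabine starts only after it. Evaluable patients lost: 0.

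**The case against.** The strongest reply is that the entry count may not decide anything. If the Appendix 2 baseline is the count just before capecitabine, an entry ANC of 1.2 x 10^9/L says little about a value taken about a month later. The Day 1 blood draws and Cycle 2 laboratory tests give that reading some support, and the SAP definition is an analysis convention, not a dosing rule. This stands as a limit on the consequence. It does not remove the difference in thresholds, and on neither reading does the text say what a patient under the bar receives from Cycle 2.

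A second reply is that a general entry rule followed by a drug-specific rule is workable, and that Section 6.3 brings Appendix 2 in by cross-reference. This is partly right. However, Section 6.3 cites Appendix 2 for monitoring during combination treatment, not as a condition for starting it, so the bar is easy to overlook at enrollment. Inclusion criterion 10 (recovery from prior toxicity) and exclusion criterion 14 (investigator judgment) may screen out some of these patients, but neither sets a count.

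A reader might also infer more than the documents support:
- *That sites must break one rule to follow the other.* They need not. Capecitabine can be withheld while neratinib continues under Section 6.1.
- *That patients would be dosed unsafely.* The Appendix 2 bar is what prevents this.
- *That the patient must then stay on neratinib alone.* Sections 10.1 and 10.2 allow discontinuation or withdrawal at the investigator's or patient's request. Table A2.6 keeps neratinib going after capecitabine toxicity, but it addresses patients already on the combination.
- *That the platelet gap is certain.* It disappears if the 100 x 10^9/L figure governs.

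**Conclusion.** The concern holds as a minor mismatch between eligibility and treatment. For ANC above 1.0 and below 1.5 x 10^9/L it is plain on the text. For platelets above 50 and below 100 x 10^9/L it holds only if the 50,000/µl figure governs; the twofold contradiction in that row is an error on either figure.

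The consequence, two colonoscopies and 28 days of monotherapy with the combination already barred, rests on reading baseline as the pre-neratinib value. On that reading the patient would afterwards continue on neratinib alone or be withdrawn.

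Only the mBC part of 3-5 patients is exposed. The documents do not say how many patients have counts in these ranges, and the number may be zero. The primary and secondary endpoints are not affected. The point is still worth correcting, because it decides who is asked to undergo the procedures and the correction is small.

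**What to change.** In criterion 8, in both the synopsis and Section 5.2, add a line for mBC patients, to apply in place of the general count limits: exclude ANC <1.5 x 10^9/L or platelets <100 x 10^9/L. This matches both halves of the Appendix 2 bar and settles the platelet figure for that group. Section 5.2 already words one limit for mBC patients, in the AST/ALT row, so the format has a precedent. Leave the ANC limit for stage 1 to 3c patients as it is, since they receive no capecitabine, and do not lower the Appendix 2 floor.

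The cost is one line printed twice in an amendment and a slightly smaller mBC pool. Some of the patients lost would have been evaluable for the biopsy endpoint. The protocol already makes that trade in exclusion criterion 2, which turns away mBC patients with prior capecitabine.

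Stating in Section 6.3 which CBC governs the start of capecitabine, and what a patient below the floor receives, would lose no patients. On its own, though, it would still let patients enter with a count that may rule out the combination. The entry change does not deal with counts that fall during Cycle 1, nor with the platelet contradiction for stage 1 to 3c patients; both are separate corrections.
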